## PROTOCOL

Neurosteroids as Novel Therapeutic Agents for PTSD in OEF/OIF/OND Veterans

PI: [name], PhD

side effects during follow-up telephone phone calls (after study medication has been discontinued). Potential side effects will be monitored closely by the PI and MD members of the research team (Drs. [name], [name], and [name]). A participant may be asked to return for an unscheduled appointment to assess a potential side effect if clinically indicated.

**Laboratory Results:** Patients will receive a CBC, clinical chemistry panel, and GI panel at each study visit. Laboratory results that are outside of the normal range will be addressed by a member of the physician team. All labs will be reviewed by the study physician within 24 hours, and clinically relevant laboratory abnormalities will receive prompt follow-up attention. The Durham VA's Clinical Chemistry Laboratory will page the PI with any "alert" laboratory values that require immediate attention. Female patients will receive a serum pregnancy test. Male participants will receive a prostate specific antigen test (PSA).

**ECG Monitoring:** Final ECG readings issued by a cardiologist are available from the Durham VAMC Heart Station within 48 hours. Each patient will have an ECG at baseline and completion of the study. If the patient does not complete the study and withdraws prior to the final study visit, every effort will be made to obtain an ECG at the patient's last study visit. Any abnormal ECG findings will be discussed with a VA cardiologist by study physician ([name], [name], or [name]). If additional medical follow-up is suggested, we will proceed according to their recommendation. Additional potential follow-up actions may include, but are not limited to: Primary care provider notification by pager or email, the placement of a cardiology consult, a repeat ECG (if lead placement is suspected to have been suboptimal, for example), or referral to an onsite Acute Care Clinic/Emergency Department for assessment.

### B. Adequacy of Protection from Risks

**1. Recruitment and Informed Consent.** Study participants who are receiving outpatient care will be recruited from the Durham VA Medical Center by local advertising (flyers placed in VA-approved areas), via the VA Mid-Atlantic MIRECC Repository and Post-Deployment Mental Health Study, and by referral from Durham VA psychiatrists, PCPs and other providers. Potential participants who are not self-referred will be sent a recruitment letter followed by a phone call from a study member. A participant who is judged likely to meet all of the inclusion criteria and none of the exclusion criteria will meet with a member of the research team to discuss the research protocol, and to determine if the patient is capable of providing informed consent. The participant will be provided with a description (verbal and written) of the informed consent form, which includes the risks along with procedures to minimize these risks, and the participants' rights and responsibilities.

Participants will be given the opportunity to read the consent form and ask questions. Participants will be assured that participation in this research study is voluntary and that they may withdraw from the study at any time without adversely affecting their medical

## PROTOCOL

### Neurosteroids as Novel Therapeutic Agents for PTSD in OEF/OIF/OND Veterans

PI: [name], PhD

care or any benefits they might be receiving. They may also refuse to answer any research questions during interviews. Participants who are eligible for the study and choose to participate will sign the consent form in the presence of a member of the research team and a witness.

#### 2. Protection Against Risk.

a) *Physical Risk and Participant Safety*: Possible side effects from drawing blood (as mentioned above) will be attended to as usual in the phlebotomy laboratory. If a participant experiences serious adverse effects from the study medication, it will be discontinued and s/he will be withdrawn from the study. The participant will immediately be referred for appropriate evaluation and treatment. All serious adverse effects will be documented and reported as required by the FDA and local IRB committee.

b) *Emotional Distress and Participant Safety*: All participants will be carefully assessed before the study and will be made aware of emergency services. In addition, they will be closely monitored at screening and each study visit. During the informed consent process, they will be advised that the study procedures could potentially lead to distress and that they may withdraw from the study at any time without adversely affecting their medical care or any benefits they may be receiving. If a participant withdraws from the study and they are not currently in psychiatric or medical treatment, they will be referred to the appropriate mental health clinic (MHC, PTSD clinic, etc.) and/or primary care provider. If a participant is significantly distressed during a study visit and intervention is deemed appropriate, they will be walked to the emergency psychiatry clinic onsite for evaluation and treatment (including potential hospitalization if clinically indicated). [name] and the physician study team will be available by cell phone (per the schedule outlined below) at all times for any concerns regarding potential worsening psychiatric symptoms, including suicidal and homicidal ideation. In terms of risks to confidentiality, pertinent information regarding potential harm, including suicidal and homicidal intent will be shared as necessary and required by law with clinicians and/or the appropriate authorities. In such circumstances, records may be made available to authorities, even without the participant's consent. Upon completion of the study any participants not currently in psychiatric treatment will be referred for treatment as deemed appropriate.

## PROTOCOL

Neurosteroids as Novel Therapeutic Agents for PTSD in OEF/OIF/OND Veterans  
PI: [name], PhD

randomized controlled trials. Should [name] not be available, the cell phone cascade would then move to the 3rd-line physician, [name]. There will be a master schedule available that adapts the above call-schedule to the annual leave and travel schedules of the individual MDs listed in this cascade. This on-call schedule will be circulated weekly, so that the order of the call cascade is always up-to-date for any particular week (and incorporates any changes that may be necessary secondary to individual MD schedules).

The designated physician on-call will have the following responsibilities: The designated study team MD will conduct physical exams at baseline and study completion, medical chart review, determination of patient eligibility for study entry, review of all clinical laboratory results and ECG tracings within 24 hours (with ECG confirmation by a Durham VA cardiologist), assessments of potential to study medication by reviewing a structured rating assessment administered to each research participant at each study visit and by interviewing and examining the participant as clinically indicated, and will attend to any other medical issues that arise during the course of this study.

Should any emergent issues arise that require immediate medical and/or psychiatric attention, the Durham VA has fully staffed Emergency Department and Psychiatric Emergency Care (PEC) services – which provide acute medical and psychiatric care 24 hours per day/7 days per week. The PEC is staffed by a psychiatry resident, psychiatric social worker, and a VA psychiatry attending, of which [name] is available there one day a week. In addition, the Durham VA has a 28 bed, onsite inpatient psychiatric unit, staffed by three VA Mental Health Service Line psychiatry attendings, three Duke Medical Center psychiatry residents, and other mental health care professionals.]

c) *Potential Difficulties and Limitations:* One potential limitation of any pharmacological clinical trial is medication compliance. In order to increase the likelihood of patients taking study medication as prescribed, we will conduct “pill counts” of returned/unused study medication. Patients who miss more than 6 consecutive doses of medication or are less than 80% compliant will be withdrawn from the study. [In addition, serum levels of DHEA and DHEAS will be determined using GC/MS post-treatment, which will provide us with additional compliance information for individuals randomized to the DHEA treatment arm.

Blood samples for serum analysis will be collected in three red-top vacutainers at each study visit. All blood and serum samples will be de-identified. Blood will be centrifuged, and serum will be aliquoted into 1.5 ml cryovials and stored in a -80 degree freezer at the Durham VAMC. GC/MS analyses will be conducted when all participants have completed the study.] Another potential challenge with any clinical trial is patient recruitment.

d) *Data Monitoring and Confidentiality:* Reports from participants’ clinical records concerning research observations will not be made available to outside medical facilities

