### Exploratory Outcome Measures

The exploratory outcome measures will include: STI (myelin integrity); fMRI measures (amygdala and hippocampal connectivity); serum neurosteroid levels (DHEA; DHEAS; androsterone); PTSD symptom severity (CAPS-5); and other rating scale measures of co-occurring symptoms.

*Experimental Design:* The proposed design is a parallel-group, double-blind, PBO-controlled, randomized Phase 2 pilot study of adjunctive DHEA vs. PBO to determine target engagement of fear-anxiety-emotional circuit regulation and potential efficacy of DHEA in 40 OEF/OIF/OND Veterans with PTSD. Subjects will be randomized to receive a one-time oral dose of DHEA (400mg) or PBO and sustained administration of the study drug for 6 weeks. There will be a 2 week placebo lead-in period [all participants], followed by subjects continuing in the randomization block of DHEA or placebo for 6 weeks following acute administration. 40 subjects will be randomly assigned to one of two groups; assuming approximately a 20% drop-out rate, we anticipate that 32 participants will have at least one visit post-randomization and will be included in the statistical analysis plan (approximately 16 participants per group); a modified intent-to-treat approach will be utilized. The research pharmacist at the Durham VA will be responsible for randomization of participants in this study; a randomized block design will be utilized (4 participants).

*Shifted-Attention Emotion Appraisal (SEAT) Paradigm:* In order to investigate the brain basis of fear-anxiety emotional response and regulation, [name] laboratory has developed an emotion appraisal task (Klumpp et al, 2011; Sripada et al., 2013), modifying the task of Anderson et al (2003), and collaborating with [name] to evaluate the impact DHEA in healthy volunteers. My mentoring and collaborative team has thus demonstrated that the SEAT paradigm is an effective probe of neurosteroid regulatory effects (Sripada et al, 2013). The SEAT task uses compound stimuli that include emotional faces and neutral scenes. Stimuli include pictures of faces in front of buildings, as well as 20 pictures of faces or buildings alone. The face pictures represent neutral, angry, or fearful expressions, and the buildings are of indoor or outdoor portraits.

Participants are asked to respond to three different questions, in three different conditions: (1) 'Gender': whether the face is male or female; (2) 'Inside/Outside':

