### 3. Potential Risks

a) *Physical Risk*: Physical risks associated with participation in this study include the risks of drawing blood and adverse effects from the study medication. Possible side effects from drawing blood include bruising, bleeding, or pain at the injection site, and (rarely) fainting and infection. Blood draws at each visit are minimal risk. In terms of the study medication, DHEA has been well-tolerated at doses up to 1,600mg per day over several weeks of administration. Side effects exceeding placebo that have occurred in previous clinical trials with DHEA have included mild acne, hirsutism, and decreased HDL levels. If a participant develops side effects at any dose, they may be brought down to the previously tolerated dose or they may be withdrawn from the study and, as by the PI or MD members of the research team (Drs. [name], [name], and [name]), referred for evaluation and treatment. We will perform laboratories at each study visit (Chem 7, CBC, GI Panel) and an ECG at study entry and completion. No serious adverse events have been reported to date utilizing DHEA (sold as a dietary supplement over-the-counter in the U.S.). Of note, participants will NOT be tapered from their current stable medication regimen; DHEA will only be “added on” to treatment-as-usual.

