## PROTOCOL

Neurosteroids as Novel Therapeutic Agents for PTSD in OEF/OIF/OND Veterans  
PI: [name], PhD

than 40), and 3.) Female participants must have had a normal pelvic exam in within the last year. The National Cancer Institute does not recommend screening for uterine cancers and the American Cancer Society advocates that at the time of menopause women should report any unexpected bleeding or spotting to their physician. Given that endometrial biopsy and transvaginal ultrasound are not appropriate screening methods according to the National Cancer Institute, during the screening interview for this study we will obtain a detailed history related to onset of menopause (if appropriate), and whether bleeding or spotting has occurred since then; unexpected bleeding or spotting will be exclusionary. This will help guard against placing a subject in the study that may have an undiagnosed uterine cancer.

b) *Emotional Distress*: Participants may potentially experience emotional distress as a result of participating in this study. The study procedures could potentially lead to emotional distress from discussing trauma histories during PTSD assessments. Being placed in an MRI machine can at times induce feeling associated with claustrophobia. Each participant will be closely monitored for emotional distress, suicidal ideation and homicidal ideation at screening and each study visit (the Columbia Suicide Severity Rating Scale) will be administered at each study visit). If a participant becomes significantly distressed or their psychiatric symptoms worsen and intervention is deemed appropriate, they will be walked to the emergency psychiatry clinic (on site) for evaluation and treatment (including potential hospitalization). The study medication will be discontinued and they will be withdrawn from the study if the patient is hospitalized, or if medical and/or psychiatric issues take precedence over study participation.

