### Schedule of Events:

Week	0	1	2	3	4	5	6	7	8	Follow up
Study Visit	1	Phone Call	2	Phone Call	3	Phone Call	4	Phone Call	5	Phone Call
Informed Consent	X									
Demographics, Medical History	X									
Mental Health Diagnosis	X									
Physical Exam and ECG	X								X	
Clinician Administered PTSD Scale	X		X		X		X		X	
Adverse Events		X	X	X	X	X	X	X	X	X
Mental/Physical Health Assessments	X		X		X		X		X	
Suicide Assessment	X	X	X	X	X	X	X	X	X	X
Blood draw and Vital Signs	X		X		X		X		X	
Urine Drug Test	X		X		X		X		X	
Urinalysis	X		X		X		X		X	
Urine Pregnancy Test	X		X		X		X		X	
Dispense Drug or Placebo	X		X		X		X		X	
MRI			X						X	

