## PROTOCOL

Neurosteroids as Novel Therapeutic Agents for PTSD in OEF/OIF/OND Veterans  
PI: [name], PhD

- Drug accountability will be monitored throughout the study.
- Each patient will be instructed to return all study drug packaging and unused study drug at each visit.
- Records will be kept of all drug dispensed to and returned by participants throughout the study.

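### Withdrawal rules end study participation with no later CAPS-5, and the missing-data plan names no analysis that departs from missing at random, leaving the secondary Week 8 CAPS-5 contrast exposed

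*Combined protocol and SAP*

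**What the plan says.** **Rules that end participation.**
- Non-compliance (Adequacy of Protection from Risks, item c, Potential Difficulties and Limitations): "Patients who miss more than 6 consecutive doses of medication or are less than 80% compliant will be withdrawn from the study".
- Serious adverse effects of study medication (Protection Against Risk, item a): "it will be discontinued and s/he will be withdrawn from the study".
- Hospitalisation or overriding issues (Potential Risks, Emotional Distress): study medication stops and "they will be withdrawn from the study if the patient is hospitalized, or if medical and/or psychiatric issues take precedence over study participation".
- Side effects in general (Potential Risks, Physical Risk) are handled more flexibly: "they may be brought down to the previously tolerated dose or they may be withdrawn from the study".

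**A competing rule.** Treatment Compliance defines compliance per visit interval as 80% to 100% of prescribed drug. Its response to non-compliance is counselling by the investigator or coordinator. It does not mention withdrawal.

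**Assessments.** In the Schedule of Events, the row "Clinician Administered PTSD Scale" is marked only at the five study visits (Weeks 0, 2, 4, 6 and 8). There is no early-termination visit, and the follow-up call carries only adverse events and suicide assessment. For participants who leave early, ECG Monitoring says "every effort will be made to obtain an ECG" at the last visit; no symptom scale is mentioned.

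**Analysis (Data Analysis and Statistical Considerations).** The analysis set is modified intent-to-treat: everyone with at least one post-randomisation visit. CAPS-5 change is analysed by a mixed model using all available outcome data, and the test is a one-sided drug-placebo contrast at Week 8. Final interviews with drop-outs are intended to separate treatment-related drop-out from MAR. Likelihood methods or multiple imputation are used where contact fails or the interview is taken to confirm MAR, provided missingness is ignorable. Sensitivity analyses are called essential, but no method is named.

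**The concern.** Serious adverse effects, hospitalisation and poor adherence are all plausibly related to how a participant is doing. Under these rules each also ends the CAPS-5 series, so the Week 8 value is lost by design. The mixed model then predicts the missing Week 8 score from earlier scores, on the assumption that leavers would have followed the same course as similar participants who stayed. Stopping drug may itself change later scores, and with no off-drug CAPS-5 nothing in the data can show it.

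The missing-data text does not close the gap. MAR is a statement about unobserved scores given observed ones, so an interview about reasons cannot confirm it. Nor are treatment-related and MAR opposites: drop-out that depends on arm and on observed scores is both. Participants who cannot be reached, about whom least is known, receive MAR handling by default.

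At stake is the trial's main evidence on symptoms. For an as-randomised target, the Week 8 contrast is biased if the arms differ in how many leave, or in how far the leavers' true scores depart from the MAR prediction. No named analysis would reveal this.

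**Working it through.** **1. The plan's own figure.** The Experimental Design paragraph says "we anticipate that 32 participants will have at least one visit post-randomization and will be included in the statistical analysis plan", out of 40 at 20% drop-out: 40 × (1 − 0.20) = 32, about 16 per arm, which reproduces. The statistical section attaches 10% to the same 32, but 40 × (1 − 0.10) = 36. The implied 40 − 32 = 8 are participants with no post-randomisation visit. How many would leave under the three rules is not stated, and later withdrawals come on top, so the 8 does not measure this problem.

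**2. What a non-compliance exit loses.** Assumption: randomisation and the first randomised dose fall at Visit 2 (Week 2), after the two-week lead-in, so the post-randomisation CAPS-5 visits are Weeks 4, 6 and 8. Non-compliance is found from returned drug: "Each patient will be instructed to return all study drug packaging and unused study drug at each visit". Those visits already carry a CAPS-5, so the visit at which it is found is not lost.

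| Found at | CAPS-5 lost | Number lost of 3 | In analysis set |
|---|---|---|---|
| Visit 3 (Week 4) | Weeks 6, 8 | 2 | yes |
| Visit 4 (Week 6) | Week 8 | 1 | yes |
| Visit 5 (Week 8) | none | 0 | yes |

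Exits before Visit 3, mainly for hospitalisation, serious adverse effects or the optional side-effect withdrawal, fall outside the set.

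**3. Provisions counted.** CAPS-5 assessments provided for after withdrawal: 0. Named analyses that depart from MAR: 0. Comparing the mixed model with multiple imputation would satisfy the sensitivity wording although both assume MAR.

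**4. Illustrative bias.** The documents give no withdrawal counts by arm, SD or gap; all are assumed here. Let w be the number per arm without a Week 8 score (of 16), and g the amount, in SD, by which their true change is worse than the MAR prediction.

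Bias = (w_DHEA/16) × g_DHEA − (w_PBO/16) × g_PBO, positive meaning towards DHEA.

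With a common g of 0.4 to 0.8:
- equal counts: 0
- 3 v 1: (2/16) × 0.4 to 0.8 = 0.05 to 0.10 SD
- 4 v 0: (4/16) × 0.4 to 0.8 = 0.10 to 0.20 SD

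Signs reverse if the arms are swapped or the leavers do better than predicted.

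**5. Effect on a one-sided 5% test.** Two-sample noncentral t, noncentrality = bias / √(1/n₁ + 1/n₂). For 0.20 SD and 16 v 16: 0.20/√(2/16) = 0.566 on 30 df. The second row of each pair counts only observed Week 8 scores and ignores recovery from earlier visits.

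| Bias | n | Error if towards DHEA | Error if against |
|---|---|---|---|
| 0.20 | 16 v 16 | 13.7% | 1.4% |
| 0.20 | 12 v 16 | 12.8% | 1.6% |
| 0.10 | 16 v 16 | 8.6% | 2.7% |
| 0.10 | 13 v 15 | 8.3% | 2.9% |

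The plan adjusts Aim 2 for multiplicity. At an illustrative 2.5% level, 0.20 SD gives 7.9% or 0.6% (16 v 16) and 7.3% or 0.7% (12 v 16).

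**The case against.** **The non-compliance rule may not operate as written.** Treatment Compliance counsels at the same threshold, so whether a participant under 80% leaves at all is unresolved. This stands. It makes the number of exits uncertain and shows that taking such participants off drug would be the wrong remedy. The two texts still have to be reconciled, because one of them mandates withdrawal.

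**Treatment-related drop-outs are analysed.** A reader might infer that the plan has no analysis for them. The documents do not support that: anyone with a post-randomisation visit is in the set, and the likelihood model uses their observed scores. The gap is narrower: they are analysed only under MAR.

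**Ending visits can be proper.** The protocol recognises that discussing trauma in PTSD assessments can cause distress. Where medical or psychiatric issues outweigh taking part, stopping visits is legitimate. This stands, and that clause should remain.

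**The numbers are assumed.** This stands. The bias formula is true by construction, and nothing in the documents supports 4 v 0. The protocol reports good tolerability and no serious adverse events with DHEA to date, which points to few exits by that route. It would be wrong to read 13.7% as the trial's error rate.

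**It is a secondary outcome in a 40-person pilot.** Also true. A reader might infer that the main result is compromised; it is not, because the primary scan comes 2 hours after the acute dose. But with about 16 per arm a few lost scores count, and an unrecorded Week 8 score cannot be recovered.

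**Conclusion.** The concern holds within limits. Three stated rules remove participants from the study for reasons plausibly related to outcome, no CAPS-5 follows, and the missing-data text relies on MAR without a named check on it. The non-compliance rule also contradicts the protocol's own compliance section.

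The consequence is confined to the secondary Week 8 analyses, CAPS-5 above all. It is a bias only if the target is the as-randomised effect, which the modified intent-to-treat label suggests. The protocol does not say whether scores after stopping drug belong to the target. Neither size nor direction can be established: the 0 to 0.20 SD range rests wholly on assumed counts and gaps, and is zero when withdrawals and gaps are equal across arms. The plan should be changed, chiefly because the data concerned can be collected only while the trial runs.

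**What to change.** 1. **Non-compliance.** Replace the withdrawal rule with the counselling already in Treatment Compliance. Keep these participants on the visit schedule and analyse them as randomised.
2. **Serious adverse effects and hospitalisation.** Stop study drug. Where safe and with consent, invite the participant to the remaining scheduled CAPS-5 visits through Week 8. Flag off-drug scores so that an on-drug analysis remains possible. Leave the clause on issues that outweigh participation as a reason to end visits.
3. **Missing data.** Keep the interviews to record reasons, but delete the rule that an interview can confirm MAR. Keep the mixed model on all observed data as the main analysis. Make one of the promised sensitivity analyses a delta-adjusted imputation (shifts in either arm) or a placebo-based imputation, covering uncontactable and treatment-related drop-outs.

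Cost: a protocol amendment in a trial under IND, IRB and data monitoring committee oversight, a few off-drug visits on the existing schedule, and a possibly less favourable estimate.
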